13.4.2. Reporting Adverse Events to the Responsible IEC/IRB and Health Authorities

Adverse events that meet the IEC/IRB requirements for reporting must be reported within the IEC/IRB's written guidelines. Each clinical site will refer to and follow any guidelines set forth by their Approving IEC/IRB. Each clinical site will refer to and follow any guidelines set forth by their local governing Health Authorities.

The Sponsor will report applicable Adverse Events to the local health authorities according the written guidelines, including reporting timelines.

13.4.3. Event of Special Interest

None

13.5. Reporting of Pregnancy

Subjects reporting pregnancy (by self-report) during the study will be discontinued after the event is recorded as an Adverse Event. Once discontinued, pregnant participants and their fetuses will not be monitored for study related purposes.

Pregnant participants are not discontinued from contact lens or solution related studies for safety concerns, but due to general concerns relating to pregnancy and contact lens use. Specifically, pregnant women are discontinued due to fluctuations in refractive error and/or visual acuity that occur secondary to systemic hormonal changes, and not due to unforeseen health risks to the mother or fetus.

14. STATISTICAL METHODS

14.1. General Considerations

Statistical Analysis will be undertaken by the sponsor or under the authority of the sponsor. A general description of the statistical methods to be implemented in this clinical trial is outlined below. More details will be included in the stand-alone Statistical Analysis Plan (SAP). The SAP will be developed and finalized prior to database lock.

Clinical Study Protocol

Johnson & Johnson Vision Care, Inc.

All data summaries and statistical analyses will be performed using the Statistical Analysis System (SAS) software Version 9.4 or higher (SAS Institute, Cary, NC). Throughout the analysis of data, the results for each subject/eye will be used when available for summarization and statistical analysis. For efficacy endpoints, unscheduled visits will be summarized separately and will be excluded in the analysis. However, unscheduled visits will be included in the analysis of safety parameters (i.e. Lens Fit and SLFs).

Summary tables (Descriptive statistics and/or frequency tables) will be provided for all baseline variables, efficacy variables and safety variables as appropriate. Continuous variables will be summarized with descriptive statistics (n, mean, standard deviation [SD], median, minimum and maximum). Frequency count and percentage of subjects or eyes within each category will be provided for categorical data.

Efficacy endpoints will be summarized on both ITT and PP populations, while safety endpoints will be summarized on both safety and PP populations .

14.2. Sample Size Justification

This study was designed and powered to demonstrate that the Multifocal Test lens made with senofilcon A material made from the Flexible Manufacturing Platform (FMP), in its final lens design FAL100, FAL101 and FAL102 (low, mid and high ADD respectively) meets the design validation requirements for the following efficacy and safety endpoints:

- CLUE vision score at 2-week follow-up
- Binocular visual acuity (Distance, Intermediate and Near) at 2-week follow-up
- Proportion of eyes with a significant slit lamp finding (Grade 3 or higher)
- Proportion of eyes with unacceptable lens fitting

The historical data used for the sample size calculation were from 6 JJVC sponsored studies. Table 4 displays the studies, their corresponding study design and the number of subjects enrolled and completed. The investigational product in all these studies was the multifocal Test lens in its' final design (FAL100, FAL101 and FAL102) made from different manufacturing platforms.

Table 6: Historical Studies Utilized for Sample Size Calculation

Study	Study Design	Manufacturing Platform	#Enrolled	#Completed	Population	SKU
	Crossover	FMP ¹	46	43	Hyperopes	+1.00 to +4.00
	Crossover	TAM21 ²	71	61	Hyperopes	+1.00 to +4.00
	Crossover	TAM21	63	60	Myopes	-1.00 to -4.00
	Crossover	SCLM ³	45	45	Hyperopes	+1.00 to +4.00
	Parallel	MCLM ⁴	189	168	Myopes	-1.00 to -4.00
	Crossover	SCLM	40	34	Hyperopes	+1.00 to +4.00
Total			454	411		

¹FMP: Flexible Manufacturing Platform

²TAM21: Tokyo Automatic Machinery -3GT (3rd Generation Technology) manufacturing line

³SCLM: Single Cavity Lens Machine

Clinical Study Protocol

Johnson & Johnson Vision Care, Inc.

⁴MCLM: Multi Cavity Lens Machine

Summaries of efficacy data pooled across all the 6 studies are presented in Table 5. Results showed that near, intermediate and distance VA have similar variation across studies, therefore a 0.11 was utilized for the variation in the power calculation for all positions. Historical data have shown that the average CLUE vision score of Hyperopes is lower than that of myopes.

Table 7: Descriptive summary of Efficacy Endpoints Period 1 Only - 2-Week Follow-up

Endpoint	Mean	Median	Standard Deviation	Minimum	Maximum
Distance VA (3m)	-0.077	-0.100	0.1026	-0.320	0.560
Intermediate VA (64cm)	-0.054	-0.060	0.1014	-0.300	0.360
Near VAR (40cm)	0.077	0.060	0.1100	-0.260	0.460
Hyperopes' CLUE Vision score	47.71	48.07	17.514	10.22	93.50
Myopes' CLUE Vision score	56.46	53.37	19.227	21.51	108.04

The proportion of eyes with Grade 3 or higher SLFs and the proportion of eyes with unacceptable lens fittings pooled across all historical studies is presented in the table below. As shown, there was only 1 unacceptable lens fitting in any of the 6 historical study while there have been 5 eyes with reported Grade 3 or higher SLFs.

Table 8: Descriptive Summary of Safety Endpoints All Available Data

Endpoint	Test n(%)
Unacceptable lens fitting	1 (0.2)
SLF Grade 3+	5 (1.4)
Total Eyes (N)	350
Total Subjects	175

%= nx100/N

Safety Analysis

Our plan for safety analysis is to incorporate historical individual subject data from the 6 studies using power prior distributions in a Bayesian framework (see section 14.5). The level of influence of historical data on current is determined by a discounting factor a_0 constrained between 0 and 1 ($0 \leq a_0 \leq 1$). $a_0 = 0$ corresponds to no borrowing of the historical data; while $a_0 = 1$ corresponds to full borrowing (See section 14.5 for more details). For this study we considered a low level of borrowing ranging by 0.1 and 0.30 based on the manufacturing platform where the historical study lens was made from. Table 7 displays the number of subjects and the degrees of borrowing that will be used in the safety analysis. The approved investigational product will be manufactured from the FMP platform; therefore, the borrowing strength is larger to lenses from the FMP platform. Furthermore, the TAM21 platform is considered equivalent with respect to lens performance and lenses from these platforms are

Clinical Study Protocol

Johnson & Johnson Vision Care, Inc.

given the same borrowing strength as those from the FMP platform. While all historical studies used the lens in its final design, lenses made from the pilot line are only given a borrowing strength of 10%.

Table 9: Degrees of Borrowing Historical Data by Manufacturing Platform

Manufacturing Platform	Number of Subjects	Level of borrowing (a_0)
FMP	23	0.3
TAM21	66	0.3
Pilot Line (SCLM, MCLM)	86	0.1

We calculated the required sample size with and without borrowing historical data. To achieve a minimum of 80% power with a 2-sided type I error rate of 5%, the required sample size with no borrowing ($a_0 = 0$) was 120 subjects (240 eyes); while the sample size with borrowing was 60 subjects (120 eyes). The sample calculation in each scenario of borrowing was conducted using a Monte Carlo simulation of 1000 trials of samples of size 120 subjects (240 eyes) were drawn from a multivariate binary distribution assuming a compound symmetric (CS) covariance structure between left and right eye from the same subject. Assuming a true proportion of eyes with grade 3 or higher SLFs of $p=0.014$ and a correlation of $\rho=0.70$ between left and right eyes. The same approach was considered for the proportion of eyes with unacceptable fitting assuming a true proportion of eyes with unacceptable fit of $p=0.01$ and a correlation of $\rho=0.80$ between left and right eyes.

The sample size was mainly driven by safety analysis, the power calculation of the efficacy analysis showed that a sample size of 60 subjects is sufficiently large to test the efficacy hypotheses. No borrowing was considered for the primary efficacy analysis. Table 8 summarize the statistical power of a sample size of 60 subjects (120 eyes) for all endpoints.

Table 10: Power Calculation by Endpoint/Hypothesis Assuming a Sample Size of 60 Subjects

Endpoint	Borrowing	Hypothesis (H_A)	Power (%)
Grade 3 or Higher SLFs	Yes	$p_t < 0.05$	80
Unacceptable lens tit	Yes	$p_t < 0.05$	90
VA Distance	No	$\mu_t < +0.10$	> 99
VA Intermediate	No	$\mu_t < +0.17$	> 99
VA Near	No	$\mu_t < +0.17$	> 99
CLUE Vision (Hyperopes)	No	$\mu_t \geq 32$	99
CLUE Vision (Myopes)	No	$\mu_t \geq 40$	99

The power calculation of the efficacy analyses (CLUE and VA) was conducted using historical data presented in Table 5 above using PROC POWER for one sample means test for equivalence to test each hypothesis.

The plan is to enroll 80 eligible subjects with a target completion of 60 subjects. During the enrollment period, the subject drop-out rate will be closely monitored, if an unexpectedly high

Clinical Study Protocol

Johnson & Johnson Vision Care, Inc.

dropout rate is observed, then the targeted total enrollment number maybe be increased accordingly to ensure that a minimum of 60 subjects complete the study.

14.3. Analysis Populations

Safety Population:

All subjects who were administered any test article excluding subjects who drop out prior to administering any test article. At least one observation should be recorded.

Per-Protocol Population:

All subjects who have successfully completed all visits and did not substantially deviate from the protocol as determined by the trial cohort review committee prior to database hard lock (Per-Protocol Population). Justification of excluding subjects with protocol deviations in the per-protocol population set will be documented in a memo to file.

Intent-to-Treat (ITT) Population:

All randomized subjects regardless of actual treatment and subsequent withdrawal from study or deviation from protocol. At least one observation should be recorded.

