5.2. Masking

This is a single arm study and all subjects will be assigned to the same study lens. Subjects will be unaware of the identity of the investigational product. Investigators and clinical site personnel involved in the data collection will not be masked as to the identity of the investigational product.

Under normal circumstances, the mask should not be broken until all subjects have completed the study and the database is finalized. Otherwise, the mask should be broken only if specific emergency treatment/course of action would be dictated by knowing the treatment status of the subject. In such cases, the Investigator may, in an emergency, contact the medical monitor. In the event the mask is broken, the Sponsor must be informed as soon as possible. The date, time, and reason for the unmasking must be documented in the subject record. The Investigator is also advised not to reveal the study treatment assignment to the clinical site or Sponsor personnel.

Subjects who have had their treatment assignment unmasked are expected to return for all remaining scheduled evaluations. Subjects who are discontinued may be replaced.

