- Unacceptable Len Fit: The Null hypothesis will be rejected if the upper bound of the 2-sided 95% credible interval of the posterior estimate of the proportion of eyes with unacceptable lens fitting is below 5%.

If no SLF findings of Grade 3 or higher or unacceptable lens fit is observed, alternative analysis methods will be considered. More details will be provided in the statistical analysis plan.

Primary Efficacy Analyses:

Efficacy analysis will be conducted the Intent-to-Treat Population (ITT) without borrowing from historical data. A sensitivity analysis will be performed by incorporating historical historical data. The level of borrowing used in the safety analysis will be considered. Further sensitivity analyses on the Per-Protocol Population will also be considered.

CLUE Vision

CLUE vision scores will be analyzed using a Bayesian normal random effects model for repeated measures. The model will include baseline clue score, age, add power, gender, timepoint (3-day and 2-week follow-up evaluations) and strata (Hyperopes and Myopes) and the interaction between timepoint and strata as fixed effects. Site will be included as a random effect. An unstructured (UN) covariance structure will be used to model the residual errors from measurements within the same subject across timepoints. Heterogeneous residuals covariance structures (R-side) across strata will be considered when appropriate. Non-informative priors will be used for the unknown parameter. For the β coefficients, independent non-informative priors $N(0, 1000)$ will be used. For the variance of random effect σ_{site}^2 an independent non-informative conjugate prior inverse-gamma(0.001, 0.001) will be used. For the residual covariance structure an inverse-Wishart distribution will be used. Inferences will be carried out using the 95% posterior credible intervals for relevant parameters.

Hypothesis testing for CLUE Vision Scores endpoints will be conducted separately for each stratum:

- Hyperopes: The Null hypothesis will be rejected if the lower bound of the 2-sided 95% credible interval of the clue vision posterior mean estimate is above 32.
- Myopes: The Null hypothesis will be rejected if the lower bound of the 2-sided 95% credible interval of the clue vision posterior mean estimate is above 40.

Visual Acuity

Binocular high luminance, high contrast (HLHC) visual acuity (logMAR) at the 2-week follow-up evaluation will be analyzed using a Bayesian normal random-effects model for

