## 1. INTRODUCTION

This statistical analysis plan (SAP) describes the analyses and data presentations for protocol CR-6400 Version 4.0.

This document will serve as the final guidance for all the statistical analysis for this study and will supersede the Statistical Method section in the protocol if there are any discrepancies. Any deviation from the analysis plan will be documented as such in the clinical study report.

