### **6.4. Per-Protocol (PP)**

Per Protocol Analysis set will be the primary analysis population. It will include all subjects who have successfully completed all visits and did not substantially deviate from the protocol as determined by the trial cohort review committee prior to database hard lock. Justification of excluding subjects with protocol deviations in the per-protocol population set will be documented in a memo to file.

The following is a preliminary list of criteria that may disqualify a subject from the Per-Protocol analysis. This list is simply suggestive and is subject to change at the pre-lock review:

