## **10.2. Protocol Deviations**

Any protocol deviation that could impact the primary endpoints will result in the subject being excluded from the Per-Protocol analysis population. No analysis on protocol deviations will be performed. All reported protocol deviations will be listed.

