### **Primary Efficacy Analyses**

Efficacy analysis will be conducted the Per-Protocol Population without borrowing from historical data. A sensitivity analysis will be performed by incorporating historical data. The level of borrowing used in the safety analysis will be considered. Further sensitivity analyses on the Safety population may also be considered if the observed subject dropout rate exceeds 15%.

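### The SAP tests all five efficacy co-primaries on a Per-Protocol set whose exclusion criteria stay open until the pre-lock review, with no provision for deciding membership without sight of outcomes

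*Protocol*

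**What the plan says.** **Which set carries the efficacy tests.** SAP 6.4: "Per Protocol Analysis set will be the primary analysis population". SAP 11.1, Primary Efficacy Analyses: "Efficacy analysis will be conducted the Per-Protocol Population without borrowing from historical data". Protocol 14.5 says otherwise ("Efficacy analysis will be conducted the Intent-to-Treat Population (ITT) without borrowing from historical data"), but SAP 1 states that the SAP "will supersede the Statistical Method section in the protocol if there are any discrepancies", so Per-Protocol governs.

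**How membership is decided.** A subject must complete all visits and must not have deviated substantially, "as determined by the trial cohort review committee prior to database hard lock" (Protocol 14.3, repeated in SAP 6.4). SAP 6.4 then introduces a preliminary list of disqualifying criteria with the words "This list is simply suggestive and is subject to change at the pre-lock review". SAP 10.2 adds a second standard: "Any protocol deviation that could impact the primary endpoints will result in the subject being excluded from the Per-Protocol analysis population".

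**Design.** One arm, no randomization, the same lens for everyone. Protocol 5.2: "Investigators and clinical site personnel involved in the data collection will not be masked as to the identity of the investigational product". Each efficacy test compares a mean with a constant: CLUE 40 (myopes) and 32 (hyperopes); logMAR 0.10 (distance), 0.17 (intermediate) and 0.17 (near).

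**Checks already in the plan.** A memo to file justifies exclusions (SAP 6.4). All deviations are listed (SAP 10.2). Efficacy is summarised descriptively on both the Safety and Per-Protocol sets (SAP 8.2). An efficacy analysis on the Safety population is optional, and only if dropout exceeds 15% (SAP 11.1).

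**The concern.** In a masked randomised trial, fixing membership before lock protects the comparison because nobody can tell which exclusion favours which arm. That protection is absent here. With one arm and a fixed target, a subject's own CLUE or logMAR value shows whether keeping that subject helps or hurts.

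The two exclusion standards both need judgement, and the SAP 10.2 standard directs attention to the endpoints themselves. Data reach the central database as forms are completed (Protocol 15.1), and the sponsor reviews case report forms during the study (Protocol 16.3). So logMAR values and individual CLUE items exist, and are open to some sponsor staff, before the review takes place. Deviations may also track outcome: a subject who sees poorly may plausibly wear the lenses for less than the required 6 hours a day.

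The success rule, a posterior probability of at least 0.975, has its intended error rate only if the analysed set is chosen without regard to the outcomes. Exclusions chosen with outcomes in view, even unintentionally, move the mean towards success.

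**Working it through.** **Inputs** (Protocol 14.2, SAP 8.4): 30 completers per stratum, 60 in total. Historical CLUE mean and SD are 47.71 and 17.514 (hyperopes) and 56.46 and 19.227 (myopes). Historical VA means are -0.077, -0.054 and 0.077 logMAR, with SD 0.11 used for power. One bound of a two-sided 95% interval is used, so the error rate is 0.025 in the direction of success.

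**Step 1. The plan's own power.** One-sample t test, noncentrality = |mean - target| / SD x sqrt(n).
- Hyperopes: 15.71 / 17.514 x sqrt(30) = 4.91, power 99.7% (plan: 99).
- Myopes: 16.46 / 19.227 x sqrt(30) = 4.69, power 99.5% (plan: 99).
- Near VA, the closest VA test: 0.093 / 0.11 x sqrt(60) = 6.55, power above 99.9% (plan: > 99). Distance and intermediate are higher still.

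The stated figures reproduce.

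**Step 2. Ceiling on the effect of selective exclusion.** Draw n normal values with the true mean on the target, remove the k least favourable, and re-test the rest at the 97.5% bound (200,000 simulated trials per cell).

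| Dropped | Hyperope CLUE, n=30: false pass (mean shift) | Myope CLUE, n=30: false pass (mean shift) | VA, n=60: false pass |
|---|---|---|---|
| 0 | 2.5% | 2.5% | 2.5% |
| 1 | 6.7% (1.2) | 6.7% (1.4) | 5.5% |
| 2 | 12.9% (2.3) | 13.1% (2.5) | 9.6% |
| 3 | 21.4% (3.3) | 21.5% (3.6) | 15.3% |

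**Step 3. What this means if the lens behaves as before.** To pass, the observed mean must clear the target by 2.045 x SD / sqrt(30): 6.5 points for hyperopes and 7.2 for myopes. The historical means clear it by 15.7 and 16.5. A shift of 3 to 4 points can rescue only a result that lands just short of the bound, which is improbable at those means.

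**Step 4. Study level.** All seven hypotheses must pass, and the two safety tests use the Safety population. Take their stated powers of 80% and 90% as independent, and let the other four efficacy tests pass with certainty. The joint safety factor is then 0.80 x 0.90 = 0.72. A 21% CLUE ceiling becomes about 0.21 x 0.72 = 15%; a 6.7% ceiling becomes about 4.8%.

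**Step 5. Does the plan need the discretion?** Over an assumed 25 to 40 analysed subjects per stratum, CLUE power is 99.0% to 99.98% (hyperopes) and 98.4% to 99.95% (myopes). Neither retaining nor losing a few subjects matters for power, so there is no power reason to keep the criteria open.

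**The case against.** The best defence has four parts.

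*Deciding Per-Protocol membership before lock is normal practice, and the committee's inputs are not described.* True. A reader might infer that the committee will have every outcome in front of it. The documents do not say so: they give neither its members nor its materials, the unmasked people in Protocol 5.2 are site staff who are not said to sit on it, and a CLUE score has to be derived by item response theory. What stands is that nothing prevents access, and that the usual protection, hidden allocation, does not exist here.

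*Bias would be visible.* In part. A reader might infer that nothing could reveal selective exclusion without a control arm. SAP 8.2 contradicts that: unconditional summaries on both the Safety and Per-Protocol sets would show a moved mean, and the memo and deviation listing show who was removed. But these describe the exclusions after the fact. They neither constrain them nor re-test the hypotheses with the excluded subjects restored, and the 15% trigger for the optional analysis is dropout, not committee exclusions.

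*Low scores alone cannot lead to exclusion.* Correct. A deviation or non-completion is required, deviations must be reported within 24 hours of discovery (Protocol 10), and SAP 10.2 applies to high scorers too. This is why the table is a ceiling and not an estimate. The planned CLUE model also adjusts for baseline, age, ADD, sex and site, which the one-sample test does not.

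*The list cannot be judged.* Agreed. It is missing from the available text, possibly through removal, and its absence is not held against the plan. The criticism rests only on the statement that it may change.

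**Conclusion.** The point holds as a weakness in the SAP's rule for forming its primary efficacy set. It lies in SAP 6.4, 10.2 and 11.1 together; Protocol 14.3 shares only the committee wording, and under the Protocol's own ITT analysis the matter would be confined to a sensitivity set.

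The size is a per-endpoint ceiling: a false-pass rate rising from 2.5% to about 7%, 13% and 21% for 1, 2 or 3 of 30 CLUE subjects, and about 15% for 3 of 60 on near VA. It assumes a true mean exactly on target, normal data, a raw one-sample test, and that the worst scorers are all excludable deviators. A reader might take 21% as the chance that the study passes wrongly. The documents do not support that: all seven hypotheses must be met, the two safety co-primaries are outside the reach of Per-Protocol decisions, and the historical means lie far on the favourable side, where exclusions would hardly change the result.

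This should be corrected because the remedy is cheap and makes a positive result easier to defend, not because the trial is likely to reach a wrong conclusion without it.

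**What to change.** 1. **SAP 6.4:** replace the sentence that leaves the list open with an exclusion list fixed before any outcome review.
2. **SAP 6.4, committee procedure:** state that the committee decides from a deviation listing that omits post-dispensing CLUE and logMAR VA results, and signs off membership before any outcome summary is run. Keep in the listing the slit-lamp, fit and Snellen data needed to judge eligibility and dispensing deviations; without them the committee could not recognise some of the deviations it must rule on.
3. **SAP 6.4 and 11.1:** keep subjects with deviations not on the list in the primary set, and remove them only in a labelled sensitivity analysis.
4. **SAP 10.2:** replace the test of whether a deviation could affect a primary endpoint with a reference to the fixed list.

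The cost is SAP wording and one additional listing. The downside is that an unforeseen deviation can no longer be excluded ad hoc from the primary analysis; the sensitivity analysis in item 3 is where its effect would be shown. The change does not alter the requirement that Per-Protocol subjects complete all visits, which removes withdrawn subjects without any committee decision.
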